### 10.3 Statistical Analysis

We will use the  $Z_0$  statistic described by Nam and Kwon () in formulae (6) to derive the estimates of  $p_t$ ,  $p_c$ , and the variance of the difference between these estimates to construct the 95% 2-sided confidence interval for  $p_t - p_c$  as:

$$((\hat{p}_t - \hat{p}_c) - 1.96 \times \sqrt{\widehat{var}(\hat{p}_t - \hat{p}_c)} , (\hat{p}_t - \hat{p}_c) + 1.96 \times \sqrt{\widehat{var}(\hat{p}_t - \hat{p}_c)})$$

We will perform this analysis using the PP analysis set to test the inferiority hypothesis ( $H_{01}$ ) stated above, and if the lower bound of the interval is  $> -0.05$  we will claim non-inferiority. If and only if we reject the null ( $H_{01}$ ) hypothesis of inferiority and claim non-inferiority we will use the mITT analysis set to test the null ( $H_{02}$ ) stated below, and if the lower bound of the interval is  $> 0$  we will claim superiority.

$$\begin{aligned} H_{02}: \quad p_t &= p_c \\ H_{12}: \quad p_t &> p_c \end{aligned}$$

We will repeat the analysis described above using the as-treated (AT) analysis set as a supporting analysis of the primary outcome.

As a sensitivity analysis we will also perform the non-inferiority test using the mITT analysis set. We will also perform sensitivity analyses of the primary endpoint using a best-case and a worst-case scenario. The best-case scenario will consider nodes with missing histology to be lymphoid tissue for PINPOINT and non-lymphoid tissue for Blue dye. The worst case scenario will consider nodes with missing histology to be non-lymphoid tissue for PINPOINT and lymphoid tissue for Blue dye.

#### 10.4 Sample Size Considerations

The clinical literature provides an estimate of the expected effectiveness of LN mapping with ICG and Blue Dye. 12 studies using ICG for the purposes of LN mapping have been published (Table 1). Detection rates for LN mapping with ICG and Blue dye are reported to occur in a wide range (33-100% for ICG and 40-80% for Blue dye). A number of factors play a role in the identification of LN including tumor size, familiarity with LN mapping technique (learning curve) and obesity.

A weighted average of published LN detection rates for Blue dye and ICG (i.e., PINPOINT) in gynecological cancer suggests unilateral detection rates of 91% for ICG and 80% for Blue dye. However, we assumed LN detection rates in gynecological cancer of 84% and 80% using ICG and Blue dye, respectively. We used a lower LN detection rate of 84% for ICG and a LN detection rate at the upper end of the range for Blue dye as a conservative approach to the sample size calculation. We also assumed a non-inferiority margin of 5%.

The power calculation was performed for a 2-level hierarchical model in which nodes are nested within subject. Power was calculated as a function of the effective sample size (ESS), which is a function of the total number of nodes excised, the number of nodes within subjects (clusters), and the intra-cluster correlation (ICC). Specifically,  $ESS = n / VIF$ , where  $n$  is the total number of nodes excised across all patients, and VIF is the variance inflation factor, calculated as

$VIF = 1 + (m - 1) \times ICC$ , where  $m$  is the number of nodes per subject. Because we expect to excise 3 to 4 nodes per subject, with 150 subjects we expect to excise  $3.5 \times 150 = 525$  nodes. With 3.5 nodes per subject on average and an ICC at most 0.125 we will have VIF at most  $1 + (2 \times 3.5 - 1) \times 0.125 = 1.75$  and an ESS at least  $525 / 1.75 = 300$  nodes. Note that here  $m$  is twice the number of expected nodes per subject, since nodes will be identified using 2 different methods within the same subject. We expect the ICC to be at most 0.125 based on our estimate of the ICC = 0.07 from Crane et al..

With an ESS of at least 300 Ns we will have at least 82% power to reject  $H_{01}$  above and claim non-inferiority of PINPOINT with respect to Blue dye. This sample size calculation was

performed using nQuery Advisor ® 7.0 (Copyright © 1995-2007, Statistical Solutions, Saugus, MA). We will test the hypothesis using a two-sided 95% confidence interval (i.e., two-sided significance level of 0.05). We will enroll subjects and identify Ns using both Blue dye and PINPOINT as described above in section 8.3.1.5 until we have at least 525 LNs identified, regardless of the method used to identify them. We expect that we will enroll approximately 150 subjects to obtain 525 nodes (based on clinical literature suggesting an average of 3-4 Ns excised per subject).

## 10.5 Data Sets to be Analyzed

### 10.5.1 Per-protocol (PP)

The Per-Protocol (PP) analysis population includes all subjects that: [1] meet critical eligibility criteria, [2] have no significant protocol deviations; and [3] have evaluable assessment endpoints for the primary endpoint.

We believe that the PP population will be the population that will most likely demonstrate a difference between Blue dye and IC2000 with respect to their ability to identify lymph nodes, should a difference exist. Thus, since we are trying to show non-inferiority of IC2000 with respect to Blue dye, we believe that using the PP population for testing non-inferiority is the conservative approach

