3. Both (Fluorescent and blue)
4. Abnormal or palpably hard
5. Non-stained node found at origin or termination of fluorescent duct
6. Non-stained node found at origin or termination of blue duct
7. Non-stained node found at origin or termination of fluorescent and blue duct

Effectiveness of intraoperative Blue dye in identifying of LN will be based on the proportion of LNs identified by visualization of blue dye under white light and confirmed as lymphoid tissue by histology divided by the total number of LNs identified and excised.

Effectiveness of intraoperative PINPOINT in identifying of LN will be based on the proportion of LNs identified by PINPOINT and confirmed as lymphoid tissue by histology divided by the total number of LNs identified and excised.

Details of the surgery, including intraoperative findings will be documented. Surgical data will be collected including the ability to identify LNs, the number of LNs identified and removed, the ability to unilaterally and bilaterally map LNs, and the anatomical location and distribution of identified LNs. Failed mapping is defined as no LNs detected.

*Follow-up and Post-operative Complications:*

All Subjects will have standard of care assessments throughout the study according to the hospital/institution's standard procedures as well as study specific visits to monitor occurrence of any adverse events/adverse device effects on the date of discharge and Day 30 ( $\pm 7$  days). All subjects will be followed to monitor occurrence of adverse events up to Day 30 ( $\pm 7$  days) post-surgery. All adverse events will be followed up to Day 30 ( $\pm 7$  days). Adverse events thought to be related to the use of PINPOINT or to the LN mapping procedure will be followed until resolution or deemed chronic.

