### 8.3.1 Lymph Node Mapping Procedure

LN mapping for FIGO Clinical Stage I endometrial cancer will be performed according to the *NCCN Guidelines for Uterine Neoplasms, SLN Algorithm for Surgical Staging of Endometrial Cancer*.

LN mapping for FIGO Clinical Stage I cervical cancer will be performed according to the *NCCN Guidelines for Cervical Neoplasms, Surgical/SLN Mapping Algorithm for Early-Stage Cervical Cancer*.

In order to minimize the spillage of blue dye or IC2000 interfering with the mapping procedure when LNs are excised, mapping will be performed on one side of the pelvis

followed by the other side of the pelvis, and LN mapping with both Blue dye and PINPOINT will be completed prior to the excision of any LNs.

According to the randomization assignment, subjects randomized into the B-P Arm will be administered Blue dye first followed by the administration of IC2000. Blue dye and IC2000 will be prepared in separate syringes and administered into the cervix at the three and nine o'clock position with a superficial and deep injection. Subjects in the B-P Arm, will undergo LN mapping with Blue dye first followed by mapping with PINPOINT. LN mapping with Blue dye will be performed until the investigator identifies all blue nodes or determines that blue nodes cannot be identified. Once complete, the Investigator will begin mapping with PINPOINT until all 'IC2000' nodes are identified or the investigator determines that 'IC2000' nodes cannot be identified. Once mapping with both Blue dye and PINPOINT have been completed and documented, all LNs identified with Blue dye or PINPOINT will be excised.

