### 10.2 Hypotheses

To assess the effectiveness of PINPOINT in the identification of LNs, a non-inferiority test will be performed using the per-protocol (PP) analysis population.

$$\begin{aligned} H_{01}: \quad p_t &\leq p_c - 0.05 \\ H_{11}: \quad p_t &> p_c - 0.05 \end{aligned}$$

Here  $p_t$  and  $p_c$  represent the effectiveness of LN mapping with PINPOINT and Blue dye respectively. We define the numerator for  $p_t$  as the number of nodes identified with PINPOINT (classifications 1, 3, 5, 7 as defined in section 8.3.1.5) and confirmed as lymphoid tissue, and we define the numerator for  $p_c$  as the number of nodes identified with Blue dye (classifications 2, 3, 6, 7 as defined in section 8.3.1.5) and confirmed as lymphoid tissue. We define the denominator for both  $p_t$  and  $p_c$  as the number of nodes identified by ANY method (classifications 1-7 as defined in section 8.3.1.5). The denominator will include excised nodes confirmed as lymphoid tissue.

A non-inferiority margin of 0.05 was determined to be clinically significant based on feedback from Investigators. Within their respective groups,  $p_t$  and  $p_c$  represent the proportion of LNs identified (and confirmed to be lymphoid tissue, See [Section 8.5](#)) with PINPOINT and Blue dye respectively divided by the total number of LNs identified and excised, across all subjects.

We will repeat the analysis described above using the as-treated (AT) analysis set as a supporting analysis of the primary outcome.

As a sensitivity analysis we will also perform the non-inferiority test using the mITT analysis set. We will also perform sensitivity analyses of the primary endpoint using a best-case and a worst-case scenario. The best-case scenario will consider nodes with missing histology to be lymphoid tissue for PINPOINT and non-lymphoid tissue for Blue dye. The worst case scenario will consider nodes with missing histology to be non-lymphoid tissue for PINPOINT and lymphoid tissue for Blue dye.

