## 10.6 Secondary Objectives

The planned secondary outcomes are intended to support product labelling. We will use the step-down method described by Benjamini and Liu to control the false discovery rate at 0.05 (2-sided) while testing our secondary objectives.

The first secondary outcome is the ability of PINPOINT and Blue dye to detect at least one lymph node in a subject.

Let  $q_t$  and  $q_c$  represent the proportion of subjects with at least one lymph node identified (according to [section 8.3.1.5](#) and confirmed by histology) with PINPOINT and Blue dye respectively, divided by the total number of subjects where mapping was attempted. That is, the numerator for  $q_t$  is the number of subjects with at least 1 node identified with PINPOINT (classifications 1, 3, 5, 7) and confirmed as lymphoid tissue, and the numerator for  $q_c$  is the number of subjects with at least 1 node identified with Blue dye (classifications 2, 3, 6, 7) and confirmed as lymphoid tissue. The denominator of both  $q_t$  and  $q_c$  is the number of subjects where mapping was attempted.

The following hypotheses will be tested:

$$\begin{aligned} H_{03}: q_t &\leq q_c - 0.05 \\ H_{13}: q_t &> q_c - 0.05 \end{aligned}$$

To test this hypothesis we will estimate the difference  $q_t - q_c$  with a 95% two-sided confidence interval. We will perform this analysis using the PP analysis set to test the inferiority hypothesis ( $H_{03}$ ) stated above, and if the lower bound of the interval is greater than -0.05 we will claim non-inferiority. If and only if we reject the inferiority hypothesis ( $H_{03}$ ) we will use the mITT analysis set to test for superiority, and if the lower bound of the interval is greater than 0 we will claim superiority.

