Another secondary outcome is the bilateral LN detection rate. Let  $b_t$  and  $b_c$  represent the proportion of subjects with at least one node identified on the right side and on the left side of the pelvis and confirmed as lymphoid tissue with PINPOINT and Blue dye, respectively. That is, the numerator for  $b_t$  is the number of subjects with at least 1 node identified with PINPOINT () on the right side of the pelvis and confirmed as lymphoid tissue and at least 1 node identified with PINPOINT on the left side of the pelvis and confirmed as lymphoid tissue. Similarly, the numerator for  $b_c$  is the number of subjects with at least 1 node identified with Blue dye (classifications 2, 3, 6, 7) on the right side of the pelvis and confirmed as lymphoid tissue and at least 1 node identified with Blue dye on the left side of the pelvis and confirmed as lymphoid tissue. The denominator of both  $b_t$  and  $b_c$  is the number of subjects where mapping was attempted.

The following hypotheses will be tested:

$$\begin{aligned} H_{04}: b_t &\leq b_c - 0.05 \\ H_{14}: b_t &> b_c - 0.05 \end{aligned}$$

To test this hypothesis we will estimate the difference  $b_t - b_c$  with a 95% two-sided confidence interval. We will perform this analysis using the PP analysis set to test the inferiority hypothesis ( $H_{04}$ ) stated above, and if the lower bound of the interval is greater than -0.05 we will claim non-inferiority. If and only if we reject the inferiority hypothesis ( $H_{04}$ ) we will use the mITT analysis

set to test for superiority, and if the lower bound of the interval is greater than 0 we will claim superiority.

A third secondary outcome is the proportion of LNs identified by following lymphatic channels (ducts). Let  $d_t$  and  $d_c$  represent the proportion of nodes identified by following a duct and confirmed as lymphoid tissue with PINPOINT and Blue dye, respectively. That is, the numerator for  $d_t$  is the number of nodes identified with PINPOINT by following a duct (classifications 5, 7) and confirmed as lymphoid tissue. Similarly, the numerator for  $d_c$  is the number nodes identified with Blue dye by following a duct (classifications 6, 7) and confirmed as lymphoid tissue. We define the denominator for both  $d_t$  and  $d_c$  as the number of nodes identified by ANY method (classifications 1-7). The denominator will include excised nodes confirmed as lymphoid tissue.

The following hypotheses will be tested:

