- overall percent agreement = $100\% \times (A + D) / (A + B + C + D)$
- positive percent agreement = $100\% \times A / (A + C)$
- negative percent agreement = $100\% \times D / (B + D)$

As sensitivity analyses, we will perform the non-inferiority tests of these secondary outcomes using the mITT analysis set. We will also perform sensitivity analyses of these secondary endpoints using a best-case and a worst-case scenario. The best-case scenario will consider nodes with missing histology to be lymphoid tissue for PINPOINT and non-lymphoid tissue for Blue dye. The worst case scenario will consider nodes with missing histology to be non-lymphoid tissue for PINPOINT and lymphoid tissue for Blue dye.

The last secondary objective of the study is to find the anatomic distribution of lymph nodes. Table 8 summarizes the data to address this secondary objective. We will use Fisher's exact test to compare study arms with respect to the distribution of anatomic location of lymph nodes for each identification method. We will also use Fisher's exact test to compare identification methods with respect to the distribution of anatomic location of lymph nodes. We summarize these data using both the PP and mITT analysis sets.

Identification Method	B-P Arm		P-B Arm		Total	
	N	%	N	%	N	%
PINPOINT						
Left obturator/internal iliac						
Left external iliac						
Left common iliac						
Right obturator/internal iliac						
Right external iliac						
Right common iliac						
Presacral						
Para-aortic node below IMA						
Para-aortic node above IMA						
Other						
Blue Dye						
Left obturator/internal iliac						
Left external iliac						
Left common iliac						
Right obturator/internal iliac						
Right external iliac						
Right common iliac						
Presacral						
Para-aortic node below IMA						
Para-aortic node above IMA						
Other						
Following a Channel (No Dye Present in Node)						
Left obturator/internal iliac						
Left external iliac						
Left common iliac						
Right obturator/internal iliac						
Right external iliac						
Right common iliac						
Presacral						
Para-aortic node below IMA						
Para-aortic node above IMA						
Other						
Appearance (No Dye Present in Node)						
Left obturator/internal iliac						
Left external iliac						
Left common iliac						
Right obturator/internal iliac						
Right external iliac						
Right common iliac						
Presacral						
Para-aortic node below IMA						
Para-aortic node above IMA						
Other						

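### Does the per-protocol requirement of an evaluable primary endpoint remove failed mappings from the any-node and bilateral detection rates?

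*Protocol*

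**What the plan says.** **PP membership.** Protocol Section 10.5.1, repeated in the SAP's analysis-set definitions, sets three conditions. The third is that subjects "have evaluable assessment endpoints for the primary endpoint". The term evaluable is not defined.

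**Primary endpoint.** Section 10.2 and the SAP define a node-level proportion for each method, pooled over subjects. On the denominator they say: "The denominator will include excised nodes confirmed as lymphoid tissue".

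**Failed mapping.** Section 8.3.1 lets mapping with blue dye end when the investigator "determines that blue nodes cannot be identified", with a parallel rule for PINPOINT. Section 3.1 adds: "Failed mapping is defined as no LNs detected". Section 8.3 collects the ability to identify nodes as study data.

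**Subject-level secondary endpoints.** Section 10.6 says "The planned secondary outcomes are intended to support product labelling". The any-node rate (q) is the number of subjects with a confirmed node by the method, "divided by the total number of subjects where mapping was attempted". For the bilateral rate (b), the denominator "is the number of subjects where mapping was attempted". Non-inferiority for both is tested in PP and superiority in mITT. The SAP adds: "As sensitivity analyses, we will perform the non-inferiority tests of these secondary outcomes using the mITT analysis set".

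**Synopsis.** The Protocol Summary names PP and mITT together for the primary non-inferiority test. Section 10.3 and the SAP base the claim on PP, treat the mITT non-inferiority test as a sensitivity analysis, and open the mITT superiority test once PP non-inferiority is claimed.

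**The concern.** A subject with no confirmed node of any class adds nothing to the primary numerators or denominator. Taken alone, that subject's primary result is 0/0, and criterion [3] can be read to exclude such a subject. Yet these are exactly the failures that q and b exist to count. If they left PP, q and b would become rates among subjects in whom some node was found. They would then overstate detection for both methods, in outcomes intended for labelling. Two analysts could in principle report different PP rates from the same data.

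The synopsis seems to add a second uncertainty: if PP and mITT disagreed on the primary test, a reader of the synopsis alone might think both had to succeed.

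**Working it through.** **1. Which reading does the text support?** Three features point the same way.

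- The primary endpoint is one ratio pooled over all subjects. No per-subject proportion is defined, so 0/0 never arises in the planned calculation.
- Failing to find a node is a foreseen end of mapping, has a definition and is recorded. It is an observed result, not missing data.
- q and b carry their own denominator. Criterion [3] is worded for the primary endpoint. A specific denominator of attempted mappings would not hold in PP, the set in which these tests are run, if criterion [3] removed the failures.

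A subject whose only confirmed node is abnormal or palpably hard (class 4) has a primary denominator and stays in PP on either reading.

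**2. The primary test.** The plan's power figure reproduces. From Section 10.4: variance inflation = 1 + (2 × 3.5 − 1) × 0.125 = 1.75; effective size = 525/1.75 = 300 nodes. Power = Φ(0.09/√[(0.84 × 0.16 + 0.80 × 0.20)/300] − 1.96) = Φ(0.913) = 81.9%, against the stated 82%. The calculation counts nodes. A subject with none adds zero to both numerators and to the denominator, so the primary point estimates are the same on either reading.

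**3. Size of the effect on the rates, on the less natural reading.** Each rate is divided by (1 − f). The documents do not give f. I assume 4% and 7%, the complements of two published detection rates quoted in the protocol (96% in Table 1; 93% in Section 1.1.4). The rates are those of the three-tracer comparison in Section 1.1.4.

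| Rate | All attempts | f = 4% | f = 7% |
|---|---|---|---|
| q, ICG v blue | 87% v 71% | 90.6% v 74.0% | 93.5% v 76.3% |
| b, ICG v blue | 65% v 43% | 67.7% v 44.8% | 69.9% v 46.2% |

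For example, 0.87/0.96 = 0.906 and 0.43/0.93 = 0.462.

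**4. Effect on the non-inferiority decision.** The plan names no interval method for q and b. I assume a paired Wald interval. Let x and y be the subjects detected by PINPOINT only and by blue dye only, D = x − y, S = x + y. With n subjects,

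lower bound = [D − 1.96 √(S − D²/n)]/n.

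Subjects with no node by either method enter only through n. The numerator hardly depends on n, so a smaller n pushes the bound away from zero, and a bound already below −5 points goes further below. Discordant counts are assumed.

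| x v y | Removed from 150 | Bound, all kept | Bound, removed |
|---|---|---|---|
| 5 v 5 | 6 | −4.13 | −4.30 |
| 7 v 7 | 6 | −4.89 | −5.09 |
| 24 v 9 | 6 | +2.67 | +2.79 |
| 37 v 13 (about 87% v 71%) | 6 | +7.12 | +7.44 |
| 20 v 14 (84% v 80%) | 10 | −3.59 | −3.85 |
| 15 v 12 (82% v 80%) | 15 | −4.78 | −5.31 |

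A search over 1 to 24 subjects removed and discordant counts up to 39 each found 483 cases where a pass became a failure and none where a failure became a pass. With 6 removed and counts from 0 to 59, the decision changed only for full-denominator bounds between −4.81 and −5.00, always from pass to failure.

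**5. What else is planned.** Superiority for q and b is tested in mITT, and the SAP repeats their non-inferiority tests there. mITT leaves out aborted mappings but keeps completed mappings that found no node. Results that include these failures will therefore exist whichever way PP is read.

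**6. Synopsis.** Section 10 and the SAP also run the non-inferiority test in both sets and rank them clearly. The synopsis omits the ranking. It does not say that both must succeed.

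**The case for a change.** The best case for a change is that it costs one sentence and removes a real gap. PP decides non-inferiority for q and b, its third criterion is undefined, and the mITT analyses do not settle who belongs in PP. A rate for labelling should not depend on a choice made after the data are seen. Nor are 4% and 7% upper limits for f: a second dye and class 4 nodes lower it, while excised tissue that histology does not confirm as lymphoid raises it.

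What stands is that evaluable is undefined, that the inflation would be real on the adverse reading, and that its size is uncertain. What does not stand is that the two texts conflict. They do so only if criterion [3] is given a meaning that the explicit denominators argue against. The adverse reading would also give the sponsor no non-inferiority claim; near the margin it would lose one.

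On the synopsis, a mismatch in wording stands, but the full statistical texts agree with each other.

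**Conclusion.** No change to the plan is needed. The undefined term is a gap that the rest of the text fills sensibly: attempted mappings with no confirmed node stay in PP and count as failures for q and b. The synopsis point is a clerical looseness, and Section 10 and the SAP already agree on the decision rule.

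If the term were misread, the cost would be PP rates inflated by 1/(1 − f) for both methods, about 2 to 4 points at f = 4% and 3 to 7 points at f = 7% for the published rates used above. The primary estimates would be unchanged, and no non-inferiority claim was gained in any case searched. This rests on assumed values of f, assumed discordant counts, 150 attempted mappings and a paired Wald interval. The choice of reading rests on the text alone.
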